4.2 Premature discontinuation and missing data

A patient who prematurely discontinues from the study should have, if possible, a premature discontinuation visit with the assessment planned on the final visit. This visit should take place as soon as possible after the patient stops taking the IMP.

For patients who prematurely discontinue from the study during the COVID-19 outbreak, the premature discontinuation visit was requested by visit on site if possible, else by phone.

For these patients who prematurely discontinue from the study, evaluations performed during the premature withdrawal visit will be considered as the first unobserved scheduled visit whatever their actual dates. If the premature withdrawal visit occurs after the discontinuation of the treatment, evaluations will be reviewed during the blind review meeting prior to the database lock to confirm their use thereof.

Otherwise, missing data will not be replaced, except for sensitivity analysis of the primary endpoint (see Section 6.1.2). Based on the Last Observation Carried Forward (LOCF) method, missing values at Week 12 will be replaced by the post-randomisation last available value. For the primary efficacy endpoint, a sensitivity analysis considering the post-randomisation last available value will be performed for the contralateral eye (see Section 6.2.1).

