1.2.2 Schedule of assessments and study procedures

All patients are expected to attend 4 visits at the investigator centre during the course of the study followed by a phone call:

- Visit #1: Day -42 or Day -49 ±3 days (Screening Visit) (respectively before or after Clinical Study Protocol amendment 1 – 05JUL2019)
- Visit #2: Day 1 (Randomisation Visit)
- Visit #3: Week 6 (Day 42±3 days)
- Visit #4: Week 12 (Day 84±7 days) (Final Visit)
- Follow-up phone call: Week 16 (Day 112±7 days)

FLOW CHART: Schedule of visits and procedures

	Visit# 1 Screening Visit Day -42 or Day -49* (± 3 days)	14 or 7 days before visit#2*	Visit# 2 Randomisation Visit Day 1	Visit# 3 Day 42 (± 3 days) Week 6	Visit# 4 Final Visit or premature discontinuation visit Day 84 (± 7 days) Week 12	Follow-up Phone call Day 112 (± 7 days) Week 16
Informed consent	X					
Demography	X					
History of glaucoma or ocular hypertension	X					
Ocular medical and surgical history (other than the studied disease)	X					
Systemic medical and surgical history	X					
Previous and concomitant ocular/non ocular treatments	X					
Ocular symptoms throughout the day ⁽¹⁾	X					
Ocular symptoms upon instillation ⁽¹⁾						
Far Best Corrected Visual Acuity (BCVA)	X					
Intra-Ocular Pressure (IOP) assessment ⁽²⁾	X					
Fundus examination	X ⁽³⁾					
Central corneal thickness measurement	X ⁽³⁾					
Automated visual field	X ⁽³⁾					
Slit lamp examination ⁽⁶⁾	X					
Corneal fluorescein staining (Oxford grading scheme)	X					
Conjunctival hyperaemia (McMonnies scale)	X					
Pregnancy test ⁽⁷⁾	X					
Adverse event (AE)						
Verification of inclusion and exclusion criteria / Patient status	X					
Run-in treatment (Azopt®) dispensation ⁽⁸⁾	X					
Run-in treatment /Wash-out compliance			X			

Randomisation (IWRS)			X					
Investigational Medical Product (IMP) dispensation ⁽⁹⁾			X		X			
IMP (T4032 or Lumigan®) compliance					X		X	
Efficacy assessment by the investigator ⁽¹⁰⁾			X	X		X		
Ocular tolerance assessment by the investigator ⁽¹⁰⁾			X	X		X		
Ocular tolerance assessment by the patient ⁽¹⁰⁾			X		X		X	

*Respectively before or after Clinical Study Protocol amendment 1 – 05JUL2019

In case of premature discontinuation during the run-in/wash-out period or patient non-eligibility at visit#2, the investigator must perform the evaluations described for the randomization visit (visit #2) except to IOP measurements at 10:00 and 16:00, pregnancy test, randomization and IMP dispensation.

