4 DATA HANDLING CONVENTIONS

4.1 Visit windows

All data will be organised and analysed according to the actual observed visits.

Moreover, for IOP, the recorded value should be allocated to the most appropriate time point.

Time point	Interval of time point
08:00	Until 09:00
10:00	From 9:01 to 13:00
16:00	From 13:01

If more than one record occurs within the same timepoint then the following rule should be applied: the closest non-missing result to the scheduled timepoint should be used. To be noted as the record not used will be reclassified in another timepoint if it occurs within 30min of interval of timepoint.

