4.3.9 Compliance of T4032 or Lumigan®

Compliance will be calculated for the worse eye and the contralateral eye separately. For the calculation, the premature discontinuation is taken into account (reclassification of visits).

Compliance (%) from Day 1 to Week 6

Compliance from Day 1 to Week 6 will be calculated for each eye as follows:
((Actual number of instillations from Day 1 to Week 6) / (Theoretical number of instillations from Day 1 to Week 6) x 100 with:

- Theoretical number of instillations = (Date of Visit V3 – Date of randomisation visit), as patients should instil one drop of IMP once daily in each eye
- Maximum number of instillations = (Date of last instillation* – Date of first instillation + 1), as patients should instil one drop of IMP once daily in each eye
- Actual number of instillations:
 - If no change in the IMP instillation is recorded from Day 1 to Week 6 in the e-CRF, the actual number of instillations will be considered as equal to the maximum number of instillations
 - If changes in the IMP instillation are recorded from Day 1 to Week 6 in the e-CRF, the actual number of instillations will be equal to: Date of last instillation* – Date of first instillation + 1 – \sum Number of days with number of instillations per day in the corresponding eye=0 + \sum Number of days x (-1 + Number of instillations per day in the corresponding eye when number of instillations is >1)

Compliance (%) from Week 6 to Week 12

Compliance from Week 6 to Week 12 will be calculated for each eye, for patients not withdrawn before Week 6 as follows:

((Actual number of instillations from Week 6 to Week 12) / (Theoretical number of instillations from Week 6 to Week 12)) x 100 with:

- Theoretical number of instillations = (Date of Visit V4 – Date of V3), as patients should instil one drop of IMP once daily in each eye
- Maximum number of instillations = (Date of last instillation* – Date of first instillation + 1), as patients should instil one drop of IMP once daily in each eye
- Actual number of instillations:
 - If no change in the IMP instillation is recorded from Week 6 to Week 12 in the e-CRF, the actual number of instillations will be considered as equal to the maximum number of instillations

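### When Visit 3 was missed, a late exit visit is analysed as Week 6 and is no longer a direct Week 12 observation

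*SAP*

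**What the plan says.** SAP 4.2 asks for an exit visit with the final-visit assessments soon after the study drug is stopped. For analysis, "evaluations performed during the premature withdrawal visit will be considered as the first unobserved scheduled visit whatever their actual dates". If the exit visit falls after treatment ended, "evaluations will be reviewed during the blind review meeting prior to the database lock to confirm their use thereof".

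SAP 4.1 states "All data will be organised and analysed according to the actual observed visits" and then gives clock-time intervals for IOP. It sets no study-day windows that could override 4.2. The flow chart in SAP 1.2.2 heads its last clinic column "Visit# 4 Final Visit or premature discontinuation visit Day 84 (± 7 days) Week 12", so it places the exit visit with Week 12. SAP 4.3.9 carries the relabelling of visits into the compliance calculation.

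**The concern.** The rule works as one would expect for a patient who leaves before Visit 3. It misfires for a patient who skipped Visit 3 and left later: the label then depends on which visit happens to be empty, not on when the eye was examined. A reading taken close to Week 12 becomes a Week 6 value. The flow chart suggests the opposite label for the same visit.

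At stake are the Week 12 observed-value sensitivity analysis, the Week 12 tolerability tests, and the meaning of the Week 6 comparisons, which gain a reading taken far outside Day 42 ± 3. The sensitivity analyses in SAP 6.1.2 are meant to explore dropout. For these patients they would also differ because of a labelling artefact.

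**Working it through.** **The plan's own figure.** SAP 1.5 gives 180 per arm, SD 3 mmHg, true difference 0, margin 1.5 mmHg and a two-sided 95% CI. SE = 3 × √(2/180) = 0.316. Power per time point = Φ(1.5/0.316 − 1.96) = 0.997. Joint power over three time points with correlation 0.7 is 0.993. The stated power of more than 90% is confirmed.

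**Dates (SAP 1.2.2).** The Week 6 window is 42 ± 3 = Day 39 to 45. The Week 12 window is 84 ± 7 = Day 77 to 91. For an exit at Day 72, 72 − 42 = 30 and 84 − 72 = 12. The midpoint is (42 + 84)/2 = Day 63. Day 72 is nearer Week 12, yet SAP 4.2 makes it Week 6 if Visit 3 is empty.

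**Where that reading goes.**

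| Analysis | Use of the Day 72 reading |
|---|---|
| Primary MMRM (SAP 6.1.1) | Week 6 value; informs Week 12 through the unstructured covariance |
| LOCF ANCOVA (SAP 6.1.2) | Carried forward and used in full as Week 12 |
| Observed-value ANCOVA (SAP 6.1.2) | Excluded |
| Week 6 IOP comparisons (SAP 6.2.1) | Included as Week 6 |
| CMH tests of hyperaemia, symptoms, signs and staining (SAP 7.1 to 7.5) | Absent at Week 12, present at Week 6 |
| Visual acuity (SAP 7.6) | No Week 6 summary exists, so no table receives it unless 4.2 is applied assessment by assessment, which it does not say |
| Compliance (SAP 4.3.9) | Exit date stands in for Visit 3, so 72 − 1 = 71 days are reported as Day 1 to Week 6 |

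**Size in the MMRM.** Let N be the patients per arm, m those whose only post-baseline value is filed as Week 6, and ρ the Week 6 to Week 12 correlation. Ignoring covariates and taking SD 3 at both visits, the variance of an arm's Week 12 mean is 9/(N − m) × (1 − ρ²m/N). A misfiled value therefore keeps about ρ² of the information it would have as a Week 12 value: 0.3² = 9% to 0.9² = 81%.

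Neither m nor ρ is in the documents; the 0.7 in SAP 1.5 is between clock times, not between visits. Assumed ranges are m = 2 to 9 of 180 (1% to 5%) and ρ = 0.3 to 0.9.

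- Filed by date: SE 0.316, power 0.997.
- Misfiled, m = 2, ρ = 0.9: SE = √(2 × 9/178 × (1 − 0.81 × 2/180)) = 0.317, power 0.997.
- Misfiled, m = 9, ρ = 0.3: SE = √(2 × 9/171 × (1 − 0.09 × 9/180)) = 0.324, power 0.996.
- Observed-value ANCOVA, value dropped: SE = 3 × √(2/(180 − m)) = 0.318 to 0.324.

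With 485 randomised, about 242 per arm, power is at least 0.9997 under the same shares and correlations.

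**The case against.** A reader might infer that the reading is lost from the primary Week 12 contrast. The documents do not support that. SAP 6.1.2 keeps patients with only a Week 6 value in the MMRM, the covariance is unstructured, and LOCF restores the value in full. Only the observed-value ANCOVA drops it among the IOP analyses.

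A reader might also take an exit at about Day 80 as the typical case. That day lies inside the Visit 4 window and would ordinarily be recorded as Visit 4. The problem needs a missed Visit 3 and, most clearly, an exit after Day 63 but before Day 77.

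Nor do the documents show that this was common. SAP 4.3.3 describes a recruitment interruption and classifies patients by screening date; it does not report missed Week 6 visits. Under SAP 4.2, COVID-period exit visits could be by phone, which yields no tonometry. It is also not established that these late readings were on treatment. The flow chart appears to place the second drug dispensing at Visit 3, and off-treatment exit visits go to blind review. That review decides whether data are used; it gives no rule for changing the visit label.

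Finally, MMRM, LOCF and observed-value ANCOVA treat every patient without Week 12 data differently by design. That is correct. What stands is that here Week 12 is empty because of the label, although a reading close to Week 12 exists.

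**Conclusion.** The point holds as a minor correction. SAP 4.2 states a rule that gives the wrong label in an identifiable case, and neither 4.1 nor the blind review repairs it. The loss is complete for the observed-value ANCOVA and the Week 12 CMH safety tests, partial in the MMRM, and nil under LOCF.

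The effect on power is negligible under the assumed shares and correlations. No between-arm bias or direction is shown, so nothing here threatens the conclusion against the 1.5 mmHg margin. The number of affected patients is unknown and may be zero.

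**What to change.** Add to SAP 4.2: when Visit 3 was not observed, assign the exit visit by actual date to Week 12 if after Day 63, otherwise to Week 6, for all efficacy and safety assessments. Keep the blind review for exit visits after treatment ended. State that this rule takes precedence over the visit column in the flow chart.

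Handle compliance separately. The denominators in SAP 4.3.9 use the Visit 3 date, which does not exist for these patients if the exit visit becomes Week 12. Compute their compliance only over the single interval from Day 1 to the exit visit.

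No new data are needed: Listing 1.2 in Appendix 2 already shows the interval from Day 1 and the analysis visit. That listing subtracts the randomisation date, so Day 63 is 62 on its scale if Day 1 is the randomisation day. The change should be made before database lock.

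The cost is a short SAP text and a small programming change. The downside is that some readings before Day 77 are labelled Week 12; a Day 64 reading is 84 − 64 = 20 days early. The existing rule already does this for patients seen at Week 6 who leave soon after, for example at Day 50, and this fix leaves that case unchanged.

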4.3 Derived and transformed data

Following derived data used for analyses will be calculated.

4.3.1 Country Grouping

The patients from the following country will be pooled into one group: Canada, Hungary, Mauritius, and UK, as outsiders Countries.

After this grouping, if the model fails to converge due to low numbers of patients per treatment arm by grouping countries, other grouping should be reconsidered and explained in the footnote.

4.3.2 Baseline

Baseline will be defined for each assessment as an evaluation before the first instillation of the IMP:

- For IOP, the value recorded at 08:00 at Day 1, respectively at 10:00 and at 16:00, will be the baseline for analysis of IOP at 08:00, respectively at 10:00 and at 16:00
- For visual field, fundoscopy and corneal thickness, the value recorded at screening visit will be the baseline
- For others parameters, the value recorded at Day 1, will be the baseline for analysis

4.3.3 Possible impact of COVID-19 pandemic

To investigate the bias of recruitment before and after the recruitment interruption, patients will be classified with or without possible impact of COVID-19 pandemic based on their screening visit date respectively up to and including 18-MARS-2020, or after the 18-MAR-2020.

4.3.4 Time from diagnosis

Time from diagnosis (months) will be calculated as:

(Date of randomisation visit (Day 1) – Date of diagnosis) / 365.25 x 12.

If the day is missing and month is present the 15th day of the month will be used. If year is present and day and month are missing, the time to diagnosis will be calculated as (Year of randomisation visit (Day 1) – Year of diagnosis) x 12.

4.3.5 Wash-out duration

Wash-out duration (days) will be calculated as (Date of randomisation visit – Date of last Azopt® instillation).

4.3.6 Duration of Azopt®

Duration of Azopt® (days) will be calculated as (Date of last instillation – Date of first instillation) + 1. If the day or the month is missing for one of the dates, the duration of Azopt® will be missing.

4.3.7 Duration of T4032 or Lumigan®

Duration of T4032/Lumigan® (days) will be calculated as (Date of last instillation at Week 12 or premature discontinuation visit – Date of first instillation at Day 1) + 1. If the day or the month is missing for one of the dates, the duration of T4032/Lumigan® will be missing.

Note: This duration is also called time of exposure.

4.3.8 Compliance of Azopt®

Compliance of Azopt® will be calculated for the worse eye and the contralateral eye separately.

Compliance of Azopt® (%)

Compliance of Azopt® will be calculated for each eye as follows:

(Actual number of instillations of Azopt®) / (Theoretical number of instillations of Azopt®) x 100 with:

- Theoretical number of instillations of Azopt® = (Date of randomisation visit – 8 or – 15 (respectively before or after Clinical Study Protocol amendment 1 – 05JUL2019 based on the recorded information on the e-CRF) – Date of screening visit + 1) *2, (*2: as patients should instil one drop twice a day in each eye)
- Maximum number of instillations of Azopt® = (Date of last instillation – Date of first instillation + 1) *2, as patients should instil one drop twice a day in each eye
- Actual number of instillations:
 - If no change in Azopt® instillation is recorded in the e-CRF, the actual number of instillations will be considered as equal to the maximum number of instillations
 - If changes in Azopt® instillation are recorded in the e-CRF, the actual number of instillations will be equal to:
(Date of last instillation – Date of first instillation + 1) *2
– [$(\sum$ Number of days with number of instillations per day in the corresponding eye=0 x 2)
+ \sum Number of days with number of instillations per day in the corresponding eye=1)]
+ \sum Number of days x (Number of instillations per day in the corresponding eye when number of instillations is >2 -2)

4.3.9 Compliance of T4032 or Lumigan®

Compliance will be calculated for the worse eye and the contralateral eye separately. For the calculation, the premature discontinuation is taken into account (reclassification of visits).

Compliance (%) from Day 1 to Week 6

Compliance from Day 1 to Week 6 will be calculated for each eye as follows:
((Actual number of instillations from Day 1 to Week 6) / (Theoretical number of instillations from Day 1 to Week 6) x 100 with:

- Theoretical number of instillations = (Date of Visit V3 – Date of randomisation visit), as patients should instil one drop of IMP once daily in each eye
- Maximum number of instillations = (Date of last instillation* – Date of first instillation + 1), as patients should instil one drop of IMP once daily in each eye
- Actual number of instillations:
 - If no change in the IMP instillation is recorded from Day 1 to Week 6 in the e-CRF, the actual number of instillations will be considered as equal to the maximum number of instillations
 - If changes in the IMP instillation are recorded from Day 1 to Week 6 in the e-CRF, the actual number of instillations will be equal to: Date of last instillation* – Date of first instillation + 1 – \sum Number of days with number of instillations per day in the corresponding eye=0 + \sum Number of days x (-1 + Number of instillations per day in the corresponding eye when number of instillations is >1)

Compliance (%) from Week 6 to Week 12

Compliance from Week 6 to Week 12 will be calculated for each eye, for patients not withdrawn before Week 6 as follows:

((Actual number of instillations from Week 6 to Week 12) / (Theoretical number of instillations from Week 6 to Week 12)) x 100 with:

- Theoretical number of instillations = (Date of Visit V4 – Date of V3), as patients should instil one drop of IMP once daily in each eye
- Maximum number of instillations = (Date of last instillation* – Date of first instillation + 1), as patients should instil one drop of IMP once daily in each eye
- Actual number of instillations:
 - If no change in the IMP instillation is recorded from Week 6 to Week 12 in the e-CRF, the actual number of instillations will be considered as equal to the maximum number of instillations
 - If changes in the IMP instillation are recorded from Week 6 to Week 12 in the e-CRF, the actual number of instillations will be equal to: Date of last instillation* – Date of first instillation + 1 – \sum Number of days with number of instillations per day in the corresponding eye=0 + \sum Number of days x (-1 + Number of instillations per day in the corresponding eye when number of instillations is >1)

Compliance (%) from Day 1 to Week 12

Compliance from Day 1 to Week 12 will be calculated for each eye as follows:
((Actual number of instillations from Day 1 to Week 6 + Actual number of instillations from Week 6 to Week 12) / (Theoretical number of instillations from Day 1 to Week 6 + Theoretical number of instillations from Week 6 to Week 12)) x 100.

For patients withdrawn before Week 6, actual and theoretical numbers of instillations from Week 6 to Week 12 will not be considered for the calculation.

Individual data regarding changes in the study product instillation will be examined during a blind review meeting before database lock. In case of missing data (missing date(s), missing number of days or missing number of instillations per day), rules for calculation will be decided on a case by case basis.

* If the date of the last instillation is on/after the date of the Visit, the last date of instillation will be replaced by the day before the date of the Visit. In this case, the date of the Visit will be assumed as

the date of the first instillation for the subsequent treatment period, if applicable (i.e., for Compliance from Week 6 to Week 12).

4.3.10 Change from baseline

Change from baseline will be calculated as the difference:
Assessment at the visit – Assessment at baseline.

4.3.11 Change from baseline in classes

Change from baseline in classes will be defined as detailed below:

In four classes:

- Improvement (Decrease of score from baseline): Change from baseline <0
- Absence stable: Change from baseline = 0 and absence of symptoms
- Presence stable: Change from baseline = 0 and presence of symptoms
- Worsening (Increase of score from baseline): Change from baseline >0

In three classes compared to 0:

- Improvement (Decrease of score from baseline): Change from baseline <0
- No change: Change from baseline = 0
- Worsening (Increase of score from baseline): Change from baseline >0

In three classes compared to -1/1:

- Improvement of more than 1 point: Change from baseline <-1
- No significant change: Change from baseline \geq -1 and \leq 1
- Worsening of more than 1 point: Change from baseline >1

4.3.12 IOP value

The IOP value will be calculated for each eye as follows:

- If the first 2 readings differ by 2 mmHg or less, the mean IOP will be the average of the first 2 readings, regardless of the third reading
- If the first 2 readings differ by more than 2 mmHg and the third reading is recorded, the mean IOP will be the average of the 3 readings
- If the first 2 readings differ by more than 2 mmHg and the third reading is not recorded, the mean IOP will be the average of the first 2 readings
- If only one reading is recorded, this single reading will be used for assessment of the mean IOP

4.3.13 Mean diurnal IOP

Mean diurnal IOP will be calculated as the mean of the IOP value at 08:00, 10:00 and 16:00. If any individual IOP is missing, the mean diurnal IOP will also be missing.

Change from baseline of mean diurnal IOP will be calculated as defined in Section 4.3.10.

4.3.14 Total score of subjective ocular symptoms throughout the day

The total score of subjective ocular symptoms throughout the day (ranging from 0 to 18) will be calculated by adding the individual scores of the 6 following symptoms: irritation/burning, stinging, itching, tearing, eye dryness feeling, foreign body sensation. If any individual score is missing, the total score will also be missing.

